7.2 Safety Assessments

All patients who receive at least one dose of ipilimumab will be considered evaluable for safety parameters. Additionally, any occurrence of non-serious or SAE from time of consent forward, up to and including follow-up visits, will be reported.

Safety will be evaluated for all treated patients using the National Cancer Institute (NCI) Common Terminology Criteria for Adverse Events (CTCAE), Version 4 (<http://ctep.cancer.gov>). Safety assessments will be based on medical review of adverse event reports and the results of vital sign measurements, physical examinations, and clinical laboratory tests.

7.3 Adverse Event Reporting

An adverse event (also known as an adverse experience) is defined as any untoward medical occurrence associated with the use of a drug in humans, whether or not considered drug related. More specifically, an adverse event (can be any unfavorable and unintended sign (e.g., an abnormal laboratory finding), symptom, or disease temporally associated with the use of a drug, without any judgment about causality. An adverse event can arise from any use of the drug (e.g., off-label use, use in combination with another drug) and from any route of administration, formulation, or dose, including an overdose.

Adverse events can be spontaneously reported or elicited during open-ended questioning, examination, or evaluation of a subject. (In order to prevent reporting bias, subjects should not be questioned regarding the specific occurrence of one or more AEs.)

7.3.1 Serious Adverse Events

A *serious adverse event (SAE)* is any untoward medical occurrence that at any dose:

- results in death
- is life-threatening (defined as an event in which the subject was at risk of death at the time of the event; it does not refer to an event that hypothetically might have caused death if it were more severe)
- requires inpatient hospitalization or causes prolongation of existing hospitalization (see “note” below for exceptions)
- results in persistent or significant disability/incapacity
- is a congenital anomaly/birth defect
- Suspected transmission of an infectious agent (e.g., any organism, virus or infectious particle, pathogenic or non-pathogenic) via the study drug is an SAE.
- is an important medical event (defined as a medical event(s) that may not be immediately life-threatening or result in death or hospitalization but, based upon appropriate medical and scientific judgment, may jeopardize the subject or may require intervention [e.g., medical, surgical] to prevent one of the other serious outcomes listed in the definition above.) Examples of such events include, but are not limited to, intensive treatment in an emergency room or at home for allergic bronchospasm; blood dyscrasias or convulsions that do not result in hospitalization.)
- Although overdose and cancer are not always serious by regulatory definition, these events should be reported on an SAE form and sent to BMS in an expedited manner. An overdose is defined as the accidental or intentional ingestion or infusion of any dose of a product that is considered both excessive and medically important.

NOTE: The following hospitalizations are not considered SAEs in BMS clinical studies:

- a visit to the emergency room or other hospital department for less than 24 hours that does not result in admission (unless considered an “important medical event” or a life-threatening event)
- elective surgery, planned before signing consent
- admissions as per protocol for a planned medical/surgical procedure

- routine health assessment requiring admission for baseline/trending of health status (e.g., routine colonoscopy)
- medical/surgical admission for purpose other than remedying ill health state and was planned prior to entry into the study. Appropriate documentation is required in these cases
- admission encountered for another life circumstance that carries no bearing on health status and requires no medical/surgical intervention (e.g., lack of housing, economic inadequacy, care-giver respite, family circumstances, administrative).

Note that all pregnancies, regardless of outcome, must be reported to the sponsor on a Pregnancy Surveillance Form, not an SAE form. All pregnancies must be reported and followed to outcome, including pregnancies that occur in the female partner of a male study subject. See **Section 7.5.3 for instructions on reporting pregnancies.**

Following the subject's written consent to participate in the study, all SAEs must be collected, including those thought to be associated with protocol-specified procedures. All SAEs must be collected that occur within 70 days of discontinuation of dosing of the investigational product. If applicable, SAEs must be collected that relate to any later protocol-specified procedure (e.g., a follow-up skin biopsy). The investigator should notify BMS and Dendreon of any SAE occurring after this time period that is believed to be related to the investigational product or protocol-specified procedure.

All SAEs whether related or unrelated to the ipilimumab, must be immediately reported to BMS and Dendreon (by the investigator or designee) within 24 hours of becoming aware of the event. If only limited information is initially available, follow-up reports are required. The original SAE form must be kept on file at the study site. If the SAE occurs at a Participating Institution, the Lead Site must also be notified.

If an ongoing SAE changes in its intensity or relationship to the investigational product, a follow-up SAE report should be sent immediately to the sponsor. As follow-up information becomes available it should be sent immediately using the same procedure used for transmitting the initial SAE report. All SAEs should be followed to resolution or stabilization.

7.3.2 Significant Adverse Events

An understanding of the expected toxicities of ipilimumab suggests that the definition of "significant adverse events" (SigAEs) should exclude manageable immune related adverse events (irAEs). However, IrAEs refractory to steroid treatment will also be considered SigAEs. To evaluate the frequency of immune toxicities, patients will be assessed at baseline and monthly for immune signs and symptoms.

Significant Adverse Event (SigAE) is defined by any of the following that are attributable to therapy:

- Any \geq grade 3 or 4 non-immune-mediated toxicity (with immune-mediated toxicities defined as all irAEs listed in the ipilimumab investigators' brochure to be considered immune and per judgment of the principal investigator for events unknown as immune related adverse events).

- Any ocular toxicity considered to be immune-mediated and requiring systemic steroids.
- Any grade 3 or 4 irAEs that cannot be reduced to grade 2 or below with systemic steroids.

The following events are excluded as SigAE:

- Any toxicity attributable to androgen deprivation therapy.
- Any endocrinopathy thought to be immune-mediated where clinical symptoms are controlled with appropriate hormonal replacement therapy.
- Hospitalization for \leq grade 2 events where the reason for hospitalization is to expedite evaluation rather than to treat the toxicity.
- These criteria apply for both hematologic and non-hematologic toxicities.
- Grade 4 laboratory-only abnormalities for uric acid, WBC, and components of the WBC count.

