1.2.2.7 Drug-Related Deaths

Based on reports from the safety database as of June 30, 2009, there have been reports of death (approximately 1% [35/3800]), deemed by the investigator as possibly related to the administration of study drug. The most common cause of drug related deaths was GI perforation. Other causes included multiorgan failure, sepsis, hypotension, acidosis, and adult respiratory distress syndrome. For details on all drug-related deaths, refer to the current version of the Ipilimumab Investigator Brochure.

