9.2.2 Stopping Rules for Toxicity

A stopping rule for safety will be applied separately to each arm for the Phase 2 study. Six patients on each arm from the safety lead-in study are included in the phase II study and will have already been evaluated for safety. Within each arm, we will stop accrual if there are 3 SigAEs among the next 10 randomized patients (total accrual per arm would be 16 patients). Following these 10 patients, safety would then be assessed cumulatively and accrual will continue unless 20% or more of all treated patients on a single arm experience a SigAE as defined in section 7.3.2. If this frequency of SigAEs is observed in one arm but not in the other, then the arm with the SigAEs will be discontinued while the arm without sigAEs will continue.

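### The SigAE list behind the accrual stopping rule does not count a fatal irAE that had no documented steroid failure

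*Combined protocol and SAP*

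**What the plan says.** Section 9.2.2 (Stopping Rules for Toxicity) applies a count to each arm separately, in two stages. After the six lead-in patients, "we will stop accrual if there are 3 SigAEs among the next 10 randomized patients (total accrual per arm would be 16 patients"). From then on, "accrual will continue unless 20% or more of all treated patients on a single arm experience a SigAE", with the term taken from section 7.3.2.

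Section 7.3.2 (Significant Adverse Events) first explains that irAEs which can be managed should be left out, and then adds: "However, IrAEs refractory to steroid treatment will also be considered SigAEs". The formal definition follows as a closed list: "Significant Adverse Event (SigAE) is defined by any of the following that are attributable to therapy". It has three lines:

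- non-immune events: a greater-than-or-equal sign followed by "grade 3 or 4 non-immune-mediated toxicity";
- ocular irAEs: "Any ocular toxicity considered to be immune-mediated and requiring systemic steroids";
- all other irAEs: "Any grade 3 or 4 irAEs that cannot be reduced to grade 2 or below with systemic steroids".

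**The concern.** The non-immune line carries a greater-than-or-equal sign and so reaches grade 5. The general irAE line has no such sign, does not name grade 5, and also requires that systemic steroids failed. Read literally, an irAE that kills before steroids are given, or before their failure can be documented, meets no line of the list. Such a death is the opposite of a manageable irAE, so the wording misses the section's own aim.

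The case is foreseeable. Section 1.2.2.7 says of the ipilimumab programme: "The most common cause of drug related deaths was GI perforation". A rapidly fatal perforation may leave no steroid course to judge. The stopping rule is a count with a sharp threshold in an open-label trial, so whether such a death counts could have to be argued after the arm's tally is known.

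**Working it through.** **1. Which fatal irAEs count as the text stands**

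| Fatal irAE attributable to therapy | General irAE line | Steroid-refractory sentence | Counted? |
|---|---|---|---|
| Documented at grade 3 or 4, steroids given, not brought to grade 2 or below | met | met | yes |
| Steroids given and failed, recorded only as grade 5 | not met (grade) | met | yes, through the sentence only |
| Documented at grade 3 or 4, no steroid course or failure not documented | not met (steroid condition) | not met | not literally |
| Recorded only as grade 5, no documented steroid failure | not met (both conditions) | not met | not literally |

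Immune-mediated ocular events needing systemic steroids count at any grade. The gap is therefore the last two rows. Recording only the top grade is realistic, because section 9.3.1.1 tabulates each patient's maximum grade for each type of toxicity.

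**2. Whether another rule closes the gap**

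- Section 7.6.3.1 sends treatment-related deaths to the DSMC Chair within 1 business day but ties no accrual stop to them.
- Section 7.6.4 asks for a report when the rate of grade 3 or 4 events rises.
- The definition of unacceptable toxicity in section 3 excludes irAEs.
- Section 9.1.1 refers to DLTs defined in section 3.1, but section 3.1 defines none.

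Section 9.2.2 is thus the only numerical rule that stops an arm.

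**3. The plan's own figure**

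Accrual per arm at the end of the first stage is 6 + 10 = 16, as section 9.2.2 states. The plan gives no operating characteristics for the rule.

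**4. How often a fatal irAE might occur**

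The documents report drug-related deaths, not fatal irAEs:

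- section 1.2.2.7: 35/3800 = 0.9%;
- Table 1, grade 5 drug-related events: 20/2901 = 0.7%;
- section 1.2.4.1, the post-docetaxel prostate trial at 10 mg/kg: 4/393 = 1.0%.

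These are context only. Take an assumed fatal-irAE rate f of 1%, with a range of 0.7% to 2%. For 27 patients per arm, P(at least one) = 1 − (1 − f)^27:

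- f = 0.7%: 1 − 0.993^27 = 17.3%
- f = 1%: 1 − 0.99^27 = 23.8%
- f = 2%: 1 − 0.98^27 = 42.0%

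**5. Effect on the stopping probability**

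Assumptions: patients are independent with SigAE probability p; the six lead-in patients have no stopping rule of their own but enter the cumulative count; the first stage stops at 3 or more of the next 10. The cumulative rule is then checked after each patient from n = 16 to 27. Stopping at 20% or more means at least 4 patients with a SigAE for n = 16 to 20, 5 for n = 21 to 25, and 6 for n = 26 to 27. Stage 1 is an exact binomial tail, and the remainder is an exact patient-by-patient recursion. Counting the deaths is modelled by replacing p with p + 1%, as if none of them were counted now.

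| Base SigAE rate (assumed) | P(stop at stage 1) | P(stop by 27 patients) |
|---|---|---|
| 5% | 1.2% → 1.9% | 2.4% → 4.1% |
| 10% | 7.0% → 8.8% | 17.0% → 21.5% |
| 15% | 18.0% → 20.6% | 42.3% → 47.6% |
| 20% | 32.2% → 35.3% | 67.1% → 71.3% |

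For a 1% fatal-irAE rate these increases are upper bounds, because deaths after failed steroids already count.

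**The case against.** A reader might infer that the definition leaves every fatal irAE out of the stopping rule. The documents do not support that. The steroid-refractory sentence and the ocular line have no grade limit. An irAE that reached grade 3 or 4, was treated with systemic steroids and ended in death was never reduced to grade 2 or below, so it meets the general line as written.

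Three further objections have force.

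- **The missing sign is not the main cause.** Appendix 3 places perforation in its grade 3 to 4 column, so a perforation would normally have a grade 4 stage. What then leaves it uncounted is the steroid condition. The non-immune line is itself loosely drafted, so the absence of a sign elsewhere need not be a deliberate cap. This stands, and it determines the form of the fix.
- **The death rates are loose proxies.** They cover drug-related deaths of any kind. The 4/393 is at 10 mg/kg, whereas this trial uses 3 mg/kg, and Table 3 shows grade 3 to 4 irAEs in 7.0% at 3 mg/kg against 25.4% at 10 mg/kg. This also stands: the rates used above are assumptions, not forecasts.
- **A death would not go unnoticed.** It goes to the DSMC Chair, grade 3 to 5 events are reviewed monthly (section 7.6.3.1), and section 7.6.4 recognises that the investigator may stop enrolment for safety. That lowers the stakes but does not settle whether the death enters the count in section 9.2.2.

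**Conclusion.** The point holds in a narrow form. A fatal irAE with no steroid course, or with no documented steroid failure, is not literally a SigAE. One recorded only as grade 5 is outside the general irAE line and counts only if steroid failure is shown or the ocular line applies. This is a gap in wording that conflicts with the section's stated purpose. It is not a blanket exclusion of fatal irAEs.

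The average effect is modest. Under the assumed 1% rate and a 10% base SigAE rate, the overall chance of stopping an arm rises by at most 4.5 percentage points (21.5% − 17.0%). A single event can still decide the outcome at the boundary: as an illustration only, 3/20 = 15% continues and 4/20 = 20% stops. No sample-size or power figure depends on this point.

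**What to change.** Reconcile the irAE line and the steroid-refractory sentence in section 7.3.2 with section 9.2.2. Add a separate line to the SigAE list that counts any grade 5 event attributable to therapy, immune-mediated or not, whether or not steroids were given. Leave the steroid condition for grade 3 or 4 irAEs unchanged.

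Copying the form of the non-immune line would not work. Adding the sign alone would keep the steroid condition, so deaths before steroids would stay uncounted. Dropping that condition would count manageable grade 3 irAEs, against the section's purpose.

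The change takes a few words and alters only what is counted for accrual, not how any event is treated. Its one downside is a slightly higher chance of stopping an arm, within the bounds shown for the assumed rate.

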5.4.6 Discontinuation of Ipilimumab Treatment

The following treatment-related non-neurological adverse events require permanent discontinuation of ipilimumab:

- Any \geq Grade 2 eye pain or reduction of visual acuity that does not respond to topical therapy and does not improve to \leq Grade 1 severity within 2 weeks of starting therapy, OR requires systemic treatment.
- Any \geq Grade 3 bronchospasm or other hypersensitivity reaction.

- Any other \geq Grade 3 non-skin related adverse event with the exception of events listed below under “Exceptions to Permanent Discontinuation”.
- Any \geq Grade 4 laboratory abnormalities, except AST, ALT, or Total Bilirubin
- AST or ALT $> 5 \times$ ULN
- Total Bilirubin $> 3 \times$ ULN
- Any other \geq Grade 4 adverse event
- *Withhold of ipilimumab for greater than 60 days due to treatment related toxicity*
- Any adverse event, laboratory abnormality or intercurrent illness, which, in the judgment of the investigator, presents a substantial clinical risk to the patient with continued dosing.
- The development of progression in the global tumor burden and/or clinical deterioration of subject’s condition such that further benefit from ipilimumab dosing is unlikely or requires a change of therapy.

The following neurological adverse event requires permanent discontinuation of ipilimumab and defines unacceptable neurotoxicity:

- Any motor neurologic toxicity \geq Grade 3 regardless of causality
- Any \geq Grade 3 treatment related sensory neurologic toxicity

Please refer to the Appendices for specific treatment algorithms.

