6.1 Study Calendar

Evaluation or Treatment	Pre-study			Treatment					Follow Up		
	Proven ge 1	Proven ge 2	Proven ge 3	Pre- Ipilimum ab	Day 1 ^a +/- 3 days	Day 22 +/- 3 days	Day 43 +/- 3 days	Day 64 +/- 3 days	Day 85 +/- 3 days	Monthly for 3 months, then Q3 months ⁱ	Off Study
Serum chemistry^c				X		X	X	X	X	X	X
PSA				X	X	X	X	X	X	X	X
Urinalysis w/ micro				X		X	X	X	X		
Testosterone				X							
TSH, free T4				X	X	X	X	X	X	X	X
Blood for immune monitoring (all patients)^d				X	X ^j	X	X	X	X	X	X
CT/MRI & Bone scan^{f, g}				X ^e					X	X	
Immune Worksheet^h				X	X	X	X	X	X	X	X
Cortisol stimulation test				X							
Archived tumor tissue (if available)				X							

^a. Pre-study clinical (physical exam and performance status) and laboratory parameters are to be measured within 15 days of beginning treatment (unless otherwise indicated in section 6.2.1.1) and do not need to be repeated on Day 1.

^b. Patients randomized to Arm 1 will begin treatment with Ipilimumab 1-3 business days following the last Provenge infusion. Day 1 of the trial will be designated as the day the patient receives the first dose of ipilimumab. For patients randomized to Arm 2, Day 1 will be determined following the same parameters as Arm 1 (1-3 business days following the final Provenge infusion), with Day 22 designated as the day the patient receives the first dose of Ipilimumab

^c. SGOT, SGPT, alk phos, total bili, LDH, electrolytes (Na, K, CO₂, Cl), glucose, BUN, Cr, amylase, lipase.

^d. 60 mL in a green top tube will be collected from all patients and shipped/delivered by the Clinical Research Coordinator to [name] laboratory ([name]) for the ELISA and ELISPOT immune assays. Blood must be drawn pre-treatment. Please refer to the Lab Manual for shipping instructions for blood.

- e. Pre-study radiographic staging is to be measured within 8 weeks of beginning treatment.
- f. CT/MRI abd/pelvis is at baseline. If metastatic disease is suspected elsewhere, other imaging modalities (e.g. CT chest) are accepted to demonstrate progressive disease for eligibility. This imaging should continue with protocol-required scans throughout study participation, as indicated. If soft tissue metastatic disease is found at baseline, scans will be repeated at day 85 (+/- 7 days) and every 12 weeks (+/- 7 days) thereafter. Can also be done more often if clinically indicated.

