7.6.3 Review and Oversight Requirements

7.6.3.1 Adverse Event Monitoring

All grade(s) 3-5 adverse events, whether or not unexpected, and whether or not considered to be associated with the use of the study drug, will be entered into OnCore®, UCSF’s Clinical Trial Management System.

All grade(s) 3-5 adverse events entered into OnCore® will be reviewed on a monthly basis at the Site Committee meetings. The Site Committee will review and discuss the selected toxicity, the toxicity grade, and the attribution of relationship of the adverse event to the administration of the study drug(s).

In addition, all suspected adverse reactions considered “serious” entered into OnCore®, will be reviewed and monitored by the Data and Safety Monitoring Committee on an ongoing basis and discussed at DSMC meetings, which take place every six weeks.

If a death occurs during the treatment phase of the study or within 30 days after the last administration of the study drug(s) and it is determined to be related either to the study drug(s) or

to a study procedure, the Investigator or his/her designee must notify the DSMC Chair within 1 business day of knowledge of this event. The contact may be by phone or e-mail.

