7.6.4 Review of Adverse Event Rates

If an increase in the frequency of Grade 3 or 4 adverse events (above the rate reported in the Investigator Brochure or package insert) is noted in the study, a report should be submitted to the DSMC at the time the increased rate is identified. The report will indicate if the incidence of adverse events observed in the study is above the range stated in the Investigator Brochure or package insert.

If at any time the Investigator stops enrollment or stops the study due to safety issues, the DSMC Chair and DSMC Manager must be notified within 1 business day via e-mail. The DSMC must receive a formal letter within 10 business days and the CHR must be notified.

Data and Safety Monitoring Committee Contacts:

DSMC Chair:

Phone:

Email:

Address:

UCSF
San Francisco, CA 94115

DSMC Monitors

[REDACTED]
UCSF Helen Diller Family
Comprehensive Cancer Center
San Francisco, CA 94115

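### The SigAE definition excludes laboratory-only uric acid and white-cell abnormalities at grade 4 but not at grade 3, so the stopping counts can include the milder event and omit the worse one (minor)

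*Combined protocol and SAP*

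**What the plan says.** Section 7.3.2 defines a SigAE by several criteria, all limited to events attributable to therapy. The first is any "grade 3 or 4 non-immune-mediated toxicity". The protocol puts a greater-than-or-equal sign before these words, so the threshold is grade 3 or higher. The section also states that its criteria cover hematologic toxicities. Its list of exclusions then removes "Grade 4 laboratory-only abnormalities for uric acid, WBC, and components of the WBC count". No other section extends that exclusion to grade 3 or restores grade 4.

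Section 9.2.2 uses SigAEs for two accrual rules, each applied by arm. The first reads "Within each arm, we will stop accrual if there are 3 SigAEs among the next 10 randomized patients". After those patients, safety is assessed cumulatively: "accrual will continue unless 20% or more of all treated patients on a single arm experience a SigAE". The cumulative rule refers to Section 7.3.2 by number.

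**The concern.** A stopping count may reasonably leave out asymptomatic laboratory findings, or it may count them. It makes no sense to count the less severe grade and leave out the more severe one. Because the first rule stops an arm at three events in ten patients, one classification can decide whether accrual continues. A literal reader and a reader who guesses at intent can reach different counts from the same data.

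In practice the issue concerns white cells and their components. The study calendar schedules a CBC with differential at most visits, so these are measured repeatedly. Uric acid is named in the exclusion but is absent from the scheduled chemistry panel ("SGOT, SGPT, alk phos, total bili, LDH, electrolytes" and the analytes that follow in the calendar's footnote). The primary endpoint and the sample size are not affected.

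**Working it through.** **Step 1: apply the text.** Take a therapy-attributable, non-immune white-cell abnormality.

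| Record | Meets inclusion? | Excluded? | Counted? |
|---|---|---|---|
| Laboratory-only, grade 3 | Yes | No | Yes |
| Laboratory-only, grade 4 with no grade 3 record | Yes | Yes | **No** |
| Laboratory-only, grade 3 and then grade 4 | Yes | Only the grade 4 record | Yes, through the grade 3 record |
| Grade 4 with clinical consequences | Yes | No, not laboratory-only | Yes |

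Only the second row is out of order, so the gap is limited to patients recorded solely at grade 4.

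**Step 2: inputs.** The protocol states no operating characteristics for its stopping rules, so there is no figure to reproduce. It gives no rate for these laboratory events either. The nearest benchmark is Table 1 in Section 1.2.2.4: 127/2901 = 4.4% of patients with any drug-related grade 4 event, pooled over 0.3 to 20 mg/kg. In that population the subset at issue must be rarer, but the table covers ipilimumab and not this treatment sequence. The rates below are therefore assumptions:
- b: proportion of patients with a SigAE from another cause.
- g: proportion with only a grade 3 laboratory-only event and, separately, the same proportion with only a grade 4 one.
- The groups do not overlap, and each patient contributes at most one SigAE.

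**Step 3: the 3-in-10 rule.** P(3 or more of 10) = 1 − BinomCDF(2; 10, p), with p = b + g as written, p = b + 2g if both grades count, and p = b if both are excluded.

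| b | g | As written | Both count | Both excluded |
|---|---|---|---|---|
| 5% | 0.1% | 1.21% | 1.28% | 1.15% |
| 10% | 0.5% | 7.91% | 8.84% | 7.02% |
| 10% | 1% | 8.84% | 10.87% | 7.02% |
| 15% | 1% | 20.64% | 23.41% | 17.98% |

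Over b = 5–15% and g = 0.1–1%, the text as written falls below counting both grades by 0.07 to 2.8 percentage points, and lies above excluding both by 0.06 to 2.7 points.

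**Step 4: a wider range.** Let q be the rate of everything counted as written, from 5% to 30%, and x the rate of patients recorded only at grade 4. The stopping probability lost by leaving these patients out is 0.7 to 3.0 points at x = 1%, 1.7 to 6.1 points at x = 2%, and 5.9 to 15.2 points at x = 5%. The last value exceeds the 4.4% benchmark for all drug-related grade 4 events together.

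**Step 5: the cumulative rule.** At 27 patients, 20% is 0.20 × 27 = 5.4, so 6 patients trigger it. For a single look at n = 27 with b = 10% and g = 0.5%, P(6 or more) is 5.7% as written, 6.9% if both grades count and 4.7% if both are excluded. The rule is applied as patients accrue, so these are not overall stopping probabilities.

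**Step 6: how often the gap arises.** P(at least one grade 4-only patient in an arm of 27) = 1 − (1 − g)^27: 2.7% at g = 0.1%, 12.7% at 0.5% and 23.8% at 1%.

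**The case against.** The strongest reply is that very few patients are affected and that they are protected in other ways. The event must be attributable to therapy, non-immune, laboratory-only and recorded solely at grade 4. The safety background in Sections 1.2.2.5 and 1.2.2.6 names no white-cell abnormality; pure red cell aplasia is the only hematologic event listed, in a group each reported in under 1% of subjects. Section 5.4.6 requires permanent discontinuation for treatment-related "Grade 4 laboratory abnormalities, except AST, ALT, or Total Bilirubin". Section 7.3.1 lists blood dyscrasias without hospitalization among its examples of important medical events, so an event judged to meet that definition is an SAE and goes to both companies within 24 hours. Under Section 7.6.3.1, "All grade(s) 3-5 adverse events, whether or not unexpected", are entered in the trial database and reviewed monthly. Section 7.6.4 requires a report to the DSMC "If an increase in the frequency of Grade 3 or 4 adverse events" above the reference rate is noted. All of this stands, and it limits the consequence. None of it corrects the count that governs accrual.

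A reader might infer three stronger points, which the documents do not support:
- **That Section 5.4.6 proves the exclusion is an error, because a patient can be taken off drug for an event that is not counted.** Dosing rules and accrual rules serve different purposes, and the plan separates them deliberately elsewhere. Grade 3 enterocolitis ends treatment (Section 5.4.6 and Appendix 8), yet an irAE that steroids bring down to grade 2 or below is not a SigAE.
- **That the authors plainly meant to exclude both grades.** Nothing in the documents says so. That repair would also leave the grade 4-only patients uncounted and make the rule less sensitive.
- **That patients with severe white-cell toxicity are unprotected.** The safeguards above show otherwise.

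**Conclusion.** The rule is wrong as written. Followed literally, Section 7.3.2 feeds both stopping counts a milder event and withholds the more severe form of the same event. What cannot be established is which consistent rule was intended.

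Severity is minor. At the central assumption (10% from other causes, 0.5% at each laboratory grade) the choice moves the 3-in-10 stopping probability by about one percentage point in either direction: 8.84 − 7.91 = 0.93 points up, 7.91 − 7.02 = 0.89 points down. Calling the effect small rests on assumed rates of about 1% or less, and on equal rates at the two grades. The documents supply neither, and the difference grows with the rate. Confidence is high for the gap in the wording and lower for its size.

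**What to change.** Make the rule the same at both grades.

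**Default:** delete the grade 4 laboratory-only exclusion from Section 7.3.2, so that these abnormalities count at grade 3 and at grade 4. This does not loosen the safety rule. Its downside is that the stopping count may rise slightly.

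**Alternative:** if the sponsor and the DSMC confirm that these laboratory-only events were never meant to count, extend the exclusion to *grade 3 or 4*. The amendment should then acknowledge that the rule becomes less sensitive and that events now counted would be removed from a safety count in an open-label trial.

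The choice should be made and recorded before events are re-tabulated by arm, and then applied to all grade 3–5 events already in the database. The cost is one phrase and a re-classification of recorded events. No new data are needed.
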